The principal investigator, some of the co-investigators ([name]) and study coordinators will be involved in the consenting process. The other responsible personnel may inform the patients about the study but will not be involved in the consenting process.

D. How much time will be allotted to the process of consent?

When possible, we will discuss the study and obtain consent in the clinic prior to the day of the procedure or in the inpatient setting. Otherwise, consent will be obtained before the procedure; family members present will be included in the discussion. Duration of the consenting process will vary from one family to the other depending on how long it takes to answer all their questions. As much time that is needed will be allowed for the consenting discussion and process.

E. How will the process of consent be structured for subjects who are likely to be more vulnerable to coercion or undue influence?

All patients will have been seen by a member of our clinical team (Pediatric Gastroenterology) in the clinic prior to the procedure or in the inpatient setting. Patients who need a diagnostic or therapeutic endoscopy will be scheduled for the procedure. The need for an endoscopic procedure will identify them to the research team as a candidate. In some cases, the enrollment will happen in the clinic at the time the need for endoscopy is

identified, particularly when a research team member is seeing the patient. In other cases, potential subjects will be identified by review of scheduled procedures on the day of the procedure. Subjects who have not been offered participation in the study in the clinic will then be approached in the procedure unit on the day of the procedure by a member of the research team.

During enrollment, we will emphasize that we will provide the same quality of care regardless of their participation, and that no stigma will be attached to them if they prefer not to give consent.

We will involve all family members present during the consent process and will explain the consent form in detail.

Prior to signing the consent, we will ask if they have any questions and if they have fully understood the study.

We will discuss their options such as not participating if they choose.

We will also assess if a subject advocate is needed and should one be needed then one will be appointed.

F. Will non-English speaking subjects be enrolled in this research?

Yes

Describe the plan to conduct the process of informed consent in the language of the subject/parent(s)/guardian(s)/LAR

We have developed Spanish consents for this study. All of the subjects are appointed an interpreter if Spanish speaking that the CARES RN works with to see the patient. The Interpreter will also be utilized to approach the family and subject for this study. [name] is fully fluent in Spanish so he will not use an interpreter. The study coordinator will ensure an interpreter is utilized when [name] is not available.

G. How will it be determined that the subject/parent(s)/guardian(s)/LAR understood the information presented?

At the end of the consenting process, subjects, parents and legal guardians will be asked a series of questions at the appropriate grade level to ensure they fully understand the study.

We will also ask them if they have any questions. The consent form will be only signed when they have fully understood the study and voluntarily wish to participate in the study.

30. Documentation of Informed Consent and Assent

Select who will obtain consent from the subject/parent(s)/LAR.

[name]

[name]

[name]

[name]

[name]

[name]

[name]

31. Consent Forms and Study Information Sheets

Indicate the type of consent forms and study information sheets to be used in this research. Check all that apply.

Adult consent form

Legally authorized representative (LAR) consent form

- ◆ Parental/Guardian consent form
- ◆ Youth study information sheet
- ◆ Child study information sheet

Adult study information sheet (decisionally-impaired)

Screening consent form

Addendum consent form

- ◆ Other. Explain. Spanish Child Information Sheet and Spanish Parental/Adult ICF

32. Information Purposely Withheld

Will any information be purposely withheld from the subject during the research or after completion of the research?

Yes

A. What specific information will be withheld?

The arm of randomization "air" versus "CO₂" gas use for insufflation will be purposely withheld from the subjects and their family.

B. What is the justification for this non-disclosure?

To avoid all forms of bias; patients, endoscopists and anesthesiologists will be blinded to the arm of randomization; gas used for endoscopic insufflation

C. Will information that has been withheld eventually be shared with the subject?

No

1. Provide justification.

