The study only occurs during the procedure and therefore, investigators will not require female subjects or partners of male subjects to provide information if they become pregnant after the procedure/ study completion.

C. Are breast feeding women excluded from participation?

No

METHODS AND PROCEDURES

12. Methods and Procedures Applied to Human Subjects

A. Are there any evaluations or tests that will be performed for the purpose of determining subject eligibility which would not be routinely conducted as part of standard clinical care of the prospective subject?

No

B. Describe the research plan, including all procedures, interventions, evaluations and tests.

This is a double blinded prospective randomized study of pediatric patients undergoing procedures involving upper endoscopy in Childrens Hospital of Omaha.

- Children from 6 months to 19 years of age who meet the inclusion criteria would be approached for enrollment.
- Consent will be obtained and signed by all legal guardians or parents
- A verbal explanation of the study will be done to all children who are 7 years of age and neuro developmentally appropriate up to age 12 and verbal assent will be obtained by children who agree to participate in the study.
- Children who are 13 years to 19 years of age will be required to sign the consent form with their parents or legal guardians if they are willing to participate in the study.
- Patients will be randomized 1:1 for air and CO₂ using a card system by the endoscopy room/procedure nurse.
- The procedure room/ endoscopy room nurse will then randomize the patients as described below:

The nurse will receive 4 envelopes.

Each envelope will contain 25 cards marked "Air" and 25 cards marked "CO₂; Therefore, there will be a total of 100 cards marked "Air" and 100 cards marked "CO₂" in all the 4 sets of envelopes

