After it has been determined that the patient can be included in the study and the consents have been signed; the procedure nurse will open the first envelope and randomly pick either CO₂ or Air. She will then set up the insufflation gas based on the gas picked. She will cover the air and CO₂ dispensing machine so that the patient, anesthesiologist and endoscopist are all blinded to the type of insufflation gas used during the procedure. She will complete randomization using the cards in each set of envelope before moving to the next set. The endoscopy room/procedure room nurse will keep a record of patients randomized into the air or CO₂ group in a locked cabinet. She will assign arbitrary letters or numbers to the gas used so that the biostatistician who will perform the interim analysis will be blinded to the arm of

study as well.

- Data including age, gender, weight z scores, BMI, co-morbid factors and reason for endoscopy will be collected on all children enrolled in the study. Name and level of expertise of the endoscopist will be collected including the duration of both the procedure and anesthesia and any procedural or anesthesia related complications encountered during the procedure or within forty-eight hours of the procedure.
- Vital signs including heart rate, respiratory rate, blood pressure, end tidal CO₂ level and minute ventilation (tidal volume x respiratory rate) will be recorded before the procedure and continuously monitored during the procedure as per anesthesia protocol.
- Information regarding end tidal CO₂ level and minute ventilation will be recorded for both groups and compared to the pre-procedure values. We will also collect data on the type of anesthetic medications used and the presence of any of these symptoms (nausea, vomiting or headaches) after the procedure. Please also see attached flow chart below for protocol and randomization.

C. Select any of the following that apply to the research:

Phase I study

♦ Randomization

Placebo (or non-treatment arm)

Washout

Sensitive surveys or questionnaires

None of the above

Describe randomization process and schedule

This is a double blinded , randomized clinical study. Both the endoscopist and patients will be blinded to the insufflation gas used; Air or CO₂. The procedure room/ endoscopy room nurse will then randomize the patients as described below:

The nurse will receive 4 envelopes.

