Previous studies in adults have documented safety and efficacy of CO₂ for insufflation in decreasing abdominal distension and discomfort. Patients will be continuously monitored throughout the procedure. If there is any evidence of respiratory distress or other potential CO₂ complications, the endoscopist will be unblinded; and CO₂ will be turned off if it is being used. Physicians will be immediately available throughout the procedure and prior to discharge from the procedure suite. They will also be available by [contact].

B. Describe how the data collected will be monitored to ensure the safety of subjects.

Identify who will perform the ongoing data and safety analysis, and describe the frequency of data analysis. If there is an independent Data and Safety Monitoring Board (DSMB) provide the charter, or describe (1) the composition of the DSMB membership, (2) the frequency of DSMB meetings and reports.

An interim safety analysis will occur after enrollment of the first half of the subjects are enrolled; 50 subjects in the GA group and 50 subjects in the MAC group. The principal investigator and co-investigators will take part in this analysis.

C. Describe the auditing plan for research conducted. Identify who will conduct the

audits and specify the audit frequency.

The principal investigator will conduct auditing of the data after every 50 subjects enrolled in the study.

D. Describe the specific subject withdrawal criteria.

If any potential risks is observed during the procedure such as with evidence of respiratory distress or other potential CO₂ complications, the endoscopist will be unblinded; and CO₂ will be turned off if it is being used and the subject will be withdrawn from the study.

E. Describe the stopping rules for the research (e.g., the specific criteria for halting or early termination of the study).

The research will be terminated early if there are significant reports of adverse events reported in an arm of the study. It will also be stopped early if significant results are reported during the interim analysis after enrollment of the first half of the subjects are enrolled. .

F. Describe plans and resources available to promptly address any subject injury.

Physicians will be immediately available throughout the procedure and prior to discharge from the procedure suite. They will also be available by [contact].

19. Potential Benefits to the Subject

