Is there the prospect for direct benefit (eg, research on diagnosis or treatment of disease)?

Yes

Describe potential benefits to the subjects that may reasonably be expected from participation in the research, if any. If there are therapeutic and non-therapeutic components of the research, address anticipated benefits to subjects that may reasonably be expected from each of these components.

Patients randomized to the CO₂ arm may benefit from less procedure pain when used during colonoscopy as a few pediatric studies have shown these benefits with the use of CO₂ for colonoscopy.

20. Potential Benefits to Society

Describe the potential benefits to society that may reasonably be expected to result from this research.

Publishing this work may encourage the use of safe and best insufflation practices in all children. If elevated end tidal CO₂ levels persist despite protection of the airway, then CO₂ use in children may be limited or restricted to only colonoscopy.

ALTERNATIVES TO PARTICIPATION

21. Alternatives to Participation

1. Describe the likely care the subject would receive at this institution were he/she not to participate in the research. If there are more than one reasonable courses of treatment briefly describe.

There is currently no standard of care at this institution regarding use of "CO₂" versus "air" as the insufflation gas. The gas of choice to be used is usually at the discretion of the endoscopist and the availability of carbon dioxide gas in the procedure room or OR.

2. Is the potential benefit of the research at least as good as the potential benefits of the alternatives described above?

Yes

3. Are there any reasonably available alternatives outside this institution which would have the potential for providing benefit to the subjects outside the research context?

No

4. Would any of the study procedures or courses of treatment in the protocol be available to the subject if they elected not to participate?

Yes

a. Explain.

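### Allocation is a hand pick of cards by the unblinded procedure nurse, with no sequence, concealment or draw log described, and the audit described could not detect a steered draw

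*Combined protocol and SAP*

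**What the plan says.** Section 12.B sets 1:1 allocation "using a card system by the endoscopy room/procedure nurse". It continues: "The nurse will receive 4 envelopes". "Each envelope will contain 25 cards marked" Air and 25 marked CO₂, which makes 100 cards per arm in all. The timing is given as "After it has been determined that the patient can be included in the study and the consents have been signed"; at that point "the procedure nurse will open the first envelope and randomly pick either" gas. Then: "She will then set up the insufflation gas based on the gas picked".

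The nurse covers the machine so that patient, anesthesiologist and endoscopist do not know the gas. She finishes one envelope before starting the next, keeps the allocation record in a locked cabinet, and codes the gases so that the biostatistician doing the interim analysis is blinded. Section 12.C repeats this description.

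The only audit is in Section 18.C: "The principal investigator will conduct auditing of the data after every 50 subjects enrolled in the study". It does not mention allocation. Section 4.A.1 says that patients whose airway plan changes in the room after consent are not randomized and are replaced. It does not say whether the card is drawn before or after that decision.

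**The concern.** Random allocation needs an order that nobody chooses, hidden until the assignment cannot be undone. Here one unblinded person supplies the order by picking, acts on the result and keeps the record of it. Nothing described ties a particular card to a particular patient before the pick. A card could be selected, or returned and redrawn, without leaving a trace. A card drawn for a patient whose airway plan then changes has no stated fate.

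If assignment came to follow patient or case type, the arms would no longer be comparable at baseline, and the difference in EtCO₂ would mix the effect of the gas with the effect of who received it. This needs no bad intent; an informal preference for matching gas to case would be enough.

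**Working it through.** **The plan's own figures.** Section 4.A.2 gives a 2 mmHg difference, SD 4.3 mmHg, two-sided alpha 0.05, 80% power, 75 per group, and 100 per group after 25% dropout.
- Normal approximation: n = 2 × (1.960 + 0.842)² × 4.3² / 2² = 72.6, so 73 per group.
- Noncentral t: power is 80.2% at 74 and 80.8% at 75 per group.
- Dropout: 75 / 0.75 = 100.
- Cards: 4 × 25 = 100 per arm.

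All of these agree with the plan. The sample size is not in question.

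**What a count check can show.** An envelope holds 25 + 25 = 50 cards and is used up before the next is opened. Its final total is 25:25 for every possible order of cards, including an order chosen card by card. A tally at the end of an envelope therefore passes whether or not draws were steered.

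**How far a draw could be moved.** If the marks can be seen, the arm can be chosen outright until one type runs out. If the draw is blind but an unwanted card is returned once, the chance of the wanted arm at the start of an envelope is 1 − 0.5 × 0.5 = 0.75 instead of 0.50.

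**Illustrative size.** Two inputs are assumptions that the documents do not supply: m, the number of patients steered, all to the same arm; and g, the amount by which their EtCO₂ differs from that of other patients for reasons unrelated to the gas.
- Bias = (m / 100) × g. Even dropout leaves the proportion unchanged.
- Standard error at 75 per arm = 4.3 × √(2/75) = 0.702 mmHg.
- Noncentrality = bias / 0.702. The false-positive rate is the two-sided rejection probability of the noncentral t on 148 degrees of freedom, with no true gas effect.

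| m of 200 | g | Bias (mmHg) | Bias / 2 mmHg target | False-positive rate |
|---|---|---|---|---|
| 10 | 0.25 SD (1.075) | 0.11 | 5% | 5.3% |
| 10 | 0.5 SD (2.15) | 0.22 | 11% | 6.1% |
| 10 | 1 SD (4.3) | 0.43 | 21.5% | 9.3% |
| 20 | 0.25 SD (1.075) | 0.22 | 11% | 6.1% |
| 20 | 1 SD (4.3) | 0.86 | 43% | 22.9% |

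The result depends on g as much as on m. At the low end the effect is negligible; at the high end it is not.

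**The case against.** The case for the existing method has real points.

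- **The draw follows eligibility and consent, and three parties are blinded.** This stands as protection against selective enrolment and against biased conduct or measurement. It does not protect against selective assignment by the person who draws.
- **The plan says the pick is random and that each envelope is completed in turn.** Read fairly, this means drawing without replacement, and a redraw would be a deviation. But nothing described would prevent or record one.
- **A reader might infer that the cards are loose and that no list exists.** The documents do not say how the cards are packed, and Section 12.B refers to a flow chart for randomization that is not in the text available. The supportable statement is that no sequence is described.
- **A reader might infer that no audit of any kind could detect steering.** That is too strong. A lost card would break the 25:25 count. Patient characteristics are collected and compared between arms (Sections 12.B and 12.E), and EtCO₂ is recorded before the procedure, so gross steering could appear as imbalance. That would raise suspicion without identifying any draw.
- **A reader might infer a motive from Section 21.1**, which says gas choice depends partly on "the availability of carbon dioxide gas in the procedure room or OR". That passage describes care outside the study and also names the endoscopist's discretion, and the endoscopist is blinded in the trial. Covering the air and CO₂ dispensing machine suggests that both gases are at hand. The documents do not show that CO₂ is lacking in study rooms or that the nurse has a preference.

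**Conclusion.** The concern holds as a weakness of method. The plan leaves assignment to a hand pick by an unblinded person who also acts on it and records it, and its audit has no reference sequence to check against. The documents do not support the inference that steering took place, and the table does not estimate any bias in this trial.

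The size is conditional. With 10 of 200 draws all steered to one arm and a gap of 0.25 to 1 SD, the bias is about 0.11 to 0.43 mmHg and the false-positive rate about 5.3% to 9.3% at 75 per arm. This rests on the plan's SD of 4.3 mmHg, steering in one direction only, even dropout, an unadjusted t-test and no true effect. The sample size is unaffected. The method should be changed because a better one is cheap and makes these assumptions unnecessary.

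**What to change.** Sections 4.A.2 and 6.A.2 show that enrolment had begun, so the change applies to all allocations not yet made.

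1. Replace the hand draw with a pre-generated 1:1 sequence that keeps the present 25/25 balance per 50. For a part-used envelope, put its remaining cards into a random order so that it still closes at 25:25.
2. Have the sequence prepared and held by someone with no role in consent, the procedure or the analysis. This should not be the biostatistician, whom Section 12.B blinds. Alternatively, use the REDCap randomization module if it is available; Section 15.A names REDCap for data storage.
3. Deliver allocations in sequentially numbered, opaque, sealed single-patient envelopes. Write the subject ID and time on each before opening, and open it only once the airway plan is final.
4. At each 50-subject audit, the list holder reconciles used envelopes with the list and reports only whether they match. The principal investigator should not do this: Section 18.B gives that role a part in the interim analysis, and Section 32.C keeps blinding until the analysis is done.
5. Record the date of the switch and which subjects were allocated by the old method.

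The cost is a few hours of preparation and a small recurring task for an existing staff member outside the trial's consent, procedure and analysis roles. The sample size, the blinding and the nurse's job of setting up and covering the machine stay as they are.

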230 subjects total (100 each group). This extra 30 subjects will allow for screen failures that occur on the study for example change in plans from use of ETT or LMA to nasal cannula in the procedure room after subjects may have been consented. They will not be randomized and need to be replaced on the study.

2. What is the statistical or other justification for the total number of subjects described above?

Sample sizes of 75 per group achieve 80% power to detect a difference of 2 mmHg between the null hypothesis that both group mean EtCO₂ measurement over the length of the monitoring period are 37.2 mmHg and the alternative hypothesis that the mean of the CO₂ group is 39.2 with an estimated within group standard deviation of 4.3 mmHg and with a significance level (alpha) of 0.05 using a two-sided two-sample t-test. To adjust for the possibility of a 25% drop out rate 100 patients per group will be enrolled.

We have also allowed 30 extra subjects due to some screen failures we have had.

5. Gender of the Subjects

A. Are there any enrollment restrictions based on gender?

No

6. Age Range of Subjects

A. Will adults be enrolled ?

Yes

1. What is the age range of the adult subjects?

The adults in this study will be 19 years old.

2. What is the rationale for selecting this age range?

As we were enrolling subjects into this study we noticed we had several 19 year old subjects still being seen by our GI Department. Therefore, they would qualify for the study. We did

not want to exclude them from participating in the study. The research will be conducted in children aged 6 months to 19 years to determine if end tidal CO₂ remains persistently elevated in intubated children undergoing upper endoscopy with CO₂ insufflation and to determine if there are changes in minute ventilation with CO₂ use during upper endoscopy.

B. Will children (18 years of age or younger) be included in this research?

Yes

1. What is the justification for inclusion of children in this research?

The research will be conducted in children aged 6 months to 18 years to determine if end tidal CO₂ remains persistently elevated in intubated children undergoing upper endoscopy with CO₂ insufflation and to determine if there are changes in minute ventilation with CO₂ use during upper endoscopy.

2. What is the age range for the child subjects, and what is the justification for selecting this age range?

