Continuous data will be reported as means with standard deviations, or medians with interquartile ranges depending if variable has normal or skewed distribution respectively. Categorical variables will be described by percentages and proportions. Comparisons of continuous data will be performed using the t-test or Wilcoxon signed-ranks test. Categorical variables will be compared using the chisq test or Fishers exact test. A probability value <.05 will be considered significant. Statistical analysis will be performed using SAS 9 statistical software (SAS Institute, Cary, NC) or Graph Pad Prism 7 for Windows (Graph pad Software, San Diego, CA).

Descriptive statistics, including counts and %, means, SD, medians, will be used to summarize patient characteristics, procedural, anesthesia and safety outcomes for the two groups. Patient characteristics, Patient safety outcomes;(MV, EtCO₂), procedural, and anesthesia outcomes will be compared between the groups using the independent sample t-test or Mann-Whitney test or Fishers exact test as appropriate to the data. Changes in these safety outcome measurements across the monitoring period between the two groups using a mixed effects model will be considered

F. Does this study involve the collection of blood, urine, saliva or other human biological material (HBM)?

No

DRUGS, BIOLOGIC DRUGS AND DEVICES

13. Drugs and Biologic Drugs

1. Does this research involve the use of drugs or biologics?

No

14. Devices

1. Does this research involve a medical device(s)?

No

CONFIDENTIALITY AND PRIVACY

15. Confidentiality and Privacy

A. Describe where research data will be stored. Check all that apply.

♦ On a secure server at UNMC, CHMC, Nebraska Medicine, and/or UNO (including REDCap)

On a secure cloud server - Specify the secured cloud serve:

On a firewall protected database accessible through the internet - Specify who has administrative responsibility for maintenance of the server:

On an encrypted, password protected local hard drive

On an encrypted, password protected portable computer

On an encrypted, password protected flash drive

♦ In hard copy

♦ Other Hard copies of the original signed consent and assent forms will be stored in a locked file cabinet, or in a lock briefcase when not in use

a. Please provide justification for use of hard copies

Hard copies of consent and assent are required and are kept as per institutional policy.

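### Allocation is balanced within four consecutive 50-card envelopes, but the between-arm tests have no envelope term; if EtCO₂ or minute ventilation differs between envelopes, a little power is lost, without bias

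*Combined protocol and SAP*

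**What the plan says.** Items 12.B and 12.C describe a card system. The nurse receives four envelopes. "Each envelope will contain 25 cards marked" Air and 25 marked CO₂, which makes 100 cards per arm in all. The envelopes are used in sequence: "She will complete randomization using the cards in each set of envelope before moving to the next set". This is blocked randomisation with four consecutive blocks of 50. The nurse is to keep a record of the gas each patient was allocated; the envelope is not mentioned as part of that record.

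Item 12.E says that patient characteristics and outcomes, including EtCO₂ and minute ventilation, will be "compared between the groups using the independent sample t-test", or by a Mann-Whitney or Fisher's exact test as suits the data. A mixed effects model is to be considered for changes across the monitoring period, which is time within one procedure. Its terms are not listed. No envelope, block or enrolment-period term appears anywhere. Significance is judged at p below .05, and no confidence interval is mentioned.

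The sample size in item 4 rests on the same unblocked comparison: "Sample sizes of 75 per group achieve 80% power to detect a difference of 2 mmHg", "with an estimated within group standard deviation of 4.3 mmHg", "with a significance level (alpha) of 0.05 using a two-sided two-sample t-test".

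**The concern.** Blocking by envelope makes the arms equal in number within each stretch of enrolment. Any difference in average EtCO₂ between stretches, for example from case mix, staff or anaesthetic practice, is therefore shared almost equally by the two arms and largely cancels from their difference. A two-sample t-test does not use this. It counts the differences between envelopes as noise, so its standard error is larger than the allocation scheme warrants.

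The error is in the conservative direction. That still deserves attention here, because item 3 hypothesises that protecting the airway will eliminate the EtCO₂ elevation and that minute ventilation will not change. In a trial that expects no difference, avoidable noise leans towards the expected answer. Power is also close to its 80% target, so there is little to spare.

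**Working it through.** **Inputs from item 4.** Difference 2 mmHg (37.2 against 39.2), SD 4.3 mmHg, two-sided alpha 0.05, 75 analysed and 100 enrolled per arm, 25% dropout. **Input from items 12.B and 12.C.** Four blocks of 25 + 25. **Assumption.** The shift R in mean EtCO₂ from first to last envelope, with the four means evenly spaced. The documents give no value.

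**1. The plan's own figure.** The normal approximation gives 73 per arm and the exact t calculation 74. At 75 per arm the power is 80.8%. Allowing for dropout, 75 / (1 − 0.25) = 100. The stated 75 and 100 reproduce.

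**2. Variance between envelopes.** Evenly spaced means lie at −R/2, −R/6, R/6 and R/2, so their variance is 5R²/36. Total variance is 4.3² = 18.49.

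**3. Half-width of the 95% interval.**
- Unadjusted: t(148 df) × 4.3 × √(2/75) = 1.976 × 0.702 = 1.388 mmHg.
- With envelope: t(145 df) × √(18.49 − 5R²/36) × √(2/75).

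| R (mmHg) | Variance between envelopes | Share of total | Half-width, unadjusted | Half-width, with envelope | Unadjusted wider by | Power by formula, unadjusted / with envelope |
|---|---|---|---|---|---|---|
| 0 | 0 | 0% | 1.388 | 1.388 | 0% | 80.8% / 80.8% |
| 1 | 0.139 | 0.8% | 1.388 | 1.383 | 0.4% | 80.8% / 81.1% |
| 2 | 0.556 | 3.0% | 1.388 | 1.367 | 1.5% | 80.8% / 81.9% |
| 4 | 2.222 | 12.0% | 1.388 | 1.302 | 6.6% | 80.8% / 85.5% |

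**4. A refinement of the power column.** The 80.8% treats envelope differences as sampling noise in the estimate. Blocking removes most of that noise from the estimate, so the unadjusted test really does slightly better. With exact balance at R = 4, the true standard error is √(18.49 − 2.222) × √(2/75) = 0.659. The unadjusted test needs a difference of about 1.388, so its power is about Φ((2 − 1.388)/0.659) = Φ(0.93), or 82.4%. The real gap to 85.5% is then about 3 points, and 80.8% against 85.5% is its upper end. At R = 2 the same step gives 81.2% against 82.0%, still about 1 point.

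**5. Cost of adjusting when there is nothing to adjust for.** In 8,000 simulated trials with 25% random loss and no shift, the full interval width averaged 2.779 mmHg with the envelope term and 2.772 without: 2.779/2.772 = 1.003, or about 0.3% wider.

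**6. Direction of the error.** In simulations without dropout and with 4.3 as the SD within envelopes, the unadjusted interval covered the truth 95.2% of the time at R = 2 and 95.9% at R = 4. Coverage is at or above nominal, so type I error is not inflated.

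**The case against.** The strongest objection is that nothing in the documents shows EtCO₂ changing over enrolment, and that with no change nothing is lost. That stands, and it is why the point is conditional.

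A reader might infer change from the widened eligibility. Item 3 records that 19-year-olds and Spanish speakers were added, and item 6 says "As we were enrolling subjects into this study we noticed we had several 19 year old subjects". The documents do not support that step. They do not place the amendment relative to the four envelopes, nothing links language to EtCO₂, and the age change adds one year to a range that starts at 6 months. Suppose, generously, that 19-year-olds made up 10% of the later envelopes and differed by a full SD. The envelope mean would move 0.1 × 4.3 = 0.43 mmHg. Split half and half, that is a variance of (0.43/2)² = 0.046, or 0.25% of 18.49, and the standard error would change by about 0.13%.

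It is also fair that large gains need large shifts. Variance shares of 5%, 10% and 15% correspond to R of about 2.6, 3.6 and 4.5 mmHg, all above the 2 mmHg target effect. An envelope term is not a complete remedy either: with a straight-line trend it removes 15/16 of the trend variance, and after dropout the balance within envelopes is only approximate.

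Finally, 12.E answers a form field that asks for a brief description, and the mixed model's terms are left open. That explains the gap but does not fill it, because that model concerns time within a procedure.

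**Conclusion.** The point holds as a small, conditional loss of precision. The analysis omits the factor by which allocation was blocked. If envelope means differ, the unadjusted test is slightly conservative: about 1.5% on interval width and 1 point of power for a 2 mmHg shift, and about 6.6% and 3 to 5 points for a 4 mmHg shift. If they do not differ, nothing is lost.

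Two stronger readings are not supported. One is that the interval is certain to be too wide: this depends on a shift that the documents do not report, and 12.E plans p-values and mentions no interval. The other is that the result is biased or the sample size wrong: blocking protects against bias, and 75 per arm gives the stated power.

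The figures assume that 4.3 mmHg is the total SD within an arm, which is the natural reading of item 4. If it were instead the SD within envelopes, the unadjusted formula power would be 79.6% at 2 mmHg and 76.2% at 4 mmHg. No SD is given for minute ventilation, so the argument carries over to it but the figures do not. This is a minor point, worth making because the remedy is nearly free.

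**What to change.** In items 12.B and 12.C, have the nurse record the envelope number (1 to 4) with each allocation. In 12.E, prespecify the between-arm comparison of EtCO₂ and of minute ventilation as a linear model with arm plus envelope as a four-level fixed factor. If the mixed model is used, put the same envelope factor in it. Report the adjusted difference with its 95% confidence interval.

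The cost is one data field and three degrees of freedom (145 instead of 148 with 75 per arm). If there is no difference between envelopes, the interval is about 0.3% wider after dropout. No further patients are needed, and neither the allocation nor the procedures change.
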